Adult patients who have undergone deceased donor liver and/or kidney transplantation will be recruited and randomized 1:1 to standard of care physician-guided dosing or PPM-guided dosing. Patients with contraindications to tacrolimus will be excluded. Following transplantation, patients will be started on a standard of care medication regimen including tacrolimus. For the first 72 hours tacrolimus will be dosed per standard of care. This allows enough data points to be gathered to allow PPM prediction. Blood tacrolimus trough levels will be taken daily. For standard of care subjects, a senior clinical pharmacist will determine the subsequent doses in consultation with the attending surgeon on call. For PPM subjects, de-identified data consisting of the daily treatment regimen details including drugs already administered, drugs to be administered, and hemodialysis or any other procedures to be performed will be sent to the PPM team at UCLA. Following analysis, the PPM team will suggest a tacrolimus dose for clinician (attending surgeon on call) approval prior to administration. In the rare instance that the UCLA team cannot arrive at a recommendation, then the subject will receive the standard of care (physician-guided) tacrolimus dose. Patients will remain on the trial until discharge from the hospital at which point they will all revert to standard of care dosing. Outcome measures will include i) fraction of days outside of target range, ii) fraction of days with large (> 2 ng/mL) deviations, and iii) ratio of area-under-the-curve outside of target range to total. Clinical safety and efficacy measures will also be monitored to ensure subject safety and to correlate trough level maintenance to clinical outcomes. These include adverse events such as neurotoxicity [documented seizures, clinically significant tremors, or imaging-confirmed posterior reversible encephalopathy syndrome (PRES)], nephrotoxicity (biopsy proven acute kidney injury or calcineurin toxicity, anuria or oliguria requiring dialysis), biopsy-proven rejection, need for repeat steroid pulse, graft loss, or death.

Statistical Analysis. Comparative analysis of the effectiveness of PPM dosing will be assessed using area-under-the-curve and variance analysis as in sub-aim 1 above. Based on our preliminary results thirty patients per group will provide greater than 90% power ($\alpha = 0.05$) to show a difference in a two-tail test.

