Feasibility, Anticipated Challenges and Proposed Solutions. The UF transplant program performs more than 150 adult liver and/or kidney transplant operations per year. This allows us to complete recruitment in less than 6 months. We do not anticipate major challenges; [name] has substantial experience working on the clinical validation of PPM. We have already successfully performed a prospective pilot study with the same protocol. Because of this we have an established protocol that is conducive to markedly improving the treatment outcomes of patients that participate in the study.

Sub-Aim 2: Comparing the pharmacokinetics of patients with high variance in tacrolimus dosing with those with low variance.

Studies in kidney transplant recipients have indicated that cytochrome P450 CYP3A5 genotype and hematocrit account for more than 60% of variability in tacrolimus pharmacokinetics. Data in liver transplant patients is less well characterized but the unexplained variability is likely higher. To examine contributors to variance in tacrolimus dosing, we will measure tacrolimus pharmacokinetics in this study and correlate the findings with donor/recipient genetics, changes in drug regimens, and clinical factors such as liver and kidney function. For each subject, at least three blood samples (pre-dose and 2 and 6 hours after the dose) will be collected on study days 2, 7, and 14. We will use these pharmacokinetic data to interpret the performance of PPM predictions and provide additional validation for our trial. Genotyping of each donor and recipient

will be performed for CYP3A5 and P-glycoprotein to look for their contribution to variance in pharmacokinetics. Both one- and two-compartment models will be evaluated.

Statistical analysis. Similar to the previous sub-aim, comparisons between the two groups will be performed using either the two-tailed Welch's t-test or Student's t-test. For nonparametric (non-normal) distributions, a two-tailed Levene's test will be used to compare variances, and a two-tailed Wilcoxon Rank Sum test will be used to compare medians. The number of subjects in this study is similar to that in the study by Gerard et al in their approach to building a model for determination of tacrolimus trough blood concentrations.

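### The arm comparison makes no planned use of troughs from the shared 72-hour standard-of-care period: a missed, nearly free gain in precision, not an error

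*Combined protocol and SAP*

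**What the plan says.** Under Research Plan, Sub-Aim 1, patients are "randomized 1:1 to standard of care physician-guided dosing or PPM-guided dosing". The treatment phase is preceded by a common period: "For the first 72 hours tacrolimus will be dosed per standard of care". The stated reason is to gather enough data for PPM to predict from; no use of these data in the analysis is described. On sampling, the same paragraph says: "Blood tacrolimus trough levels will be taken daily".

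The outcomes are per-patient summaries: the fraction of days out of range, the fraction of days with deviations above 2 ng/mL, and the share of area under the curve lying outside the range. The paragraph does not say on which day counting begins, or whether allocation is made or known before the 72 hours end.

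The Sub-Aim 1 Statistical Analysis names only area-under-the-curve and variance analysis. It rests the sample size of "thirty patients per group" on preliminary results, claiming more than 90% power at alpha 0.05 "to show a difference in a two-tail test". The actual tests appear in the Sub-Aim 2 Statistical analysis, which describes itself as similar to the preceding sub-aim: "comparisons between the two groups will be performed using either the two-tailed Welch's t-test or Student's t-test", with Levene and Wilcoxon rank sum tests for non-normal data.

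**The concern.** A patient who is far from target when PPM takes over may well have more out-of-range days afterwards, whichever arm the patient is in. If so, part of the between-patient variance in the outcome is predictable from readings the trial takes anyway, and an unadjusted test leaves that part in the error term. With 30 per arm this widens the confidence interval, and in any one trial a chance difference between arms in the early readings carries into the estimated effect.

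The power claim cannot be checked, because no effect size or SD is given and the only preliminary comparison described in the Abstract had 4 patients per arm. If the true effect is smaller than the planners hoped, extra precision is worth more.

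**Working it through.** **Inputs from the document:** 30 per arm, 1:1 allocation, two-sided alpha 0.05, power above 90%, 72 hours of common dosing, daily troughs. **Not in the document:** the effect, the SD, and rho (correlation of the early-trough summary with the later outcome). Rho is therefore varied from 0 to 0.5 as an assumption.

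**1. The plan's own figure.** Power above 90% cannot be reproduced without an effect and an SD. Back-solving the two-sample t-test (58 df, noncentrality d / sqrt(2/30), sqrt(2/30) = 0.258) for exactly 90% power gives d = 0.851 SD. This is the reference effect below.

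**2. Power with adjustment.** For a linear model on arm plus one baseline value:
- variance factor relative to the unadjusted comparison: V = (1 − rho²) × (1 + 1/56). The second term is the average cost of estimating the slope.
- noncentrality: 0.851 / sqrt(V × 2/30), referred to noncentral t on 57 df.

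| rho | V | Noncentrality | Power |
|---|---|---|---|
| unadjusted | 1 | 3.30 | 90.0% |
| 0 | 1.018 | 3.27 | 89.5% |
| 0.05 | 1.015 | 3.27 | 89.5% |
| 0.2 | 0.977 | 3.34 | 90.6% |
| 0.3 | 0.926 | 3.43 | 92.0% |
| 0.4 | 0.855 | 3.57 | 93.9% |
| 0.5 | 0.763 | 3.77 | 96.0% |

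**3. Break-even.** V = 1 when 1 − rho² = 56/57, so rho = sqrt(1/57) = 0.13. Below that, adjustment loses slightly.

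**4. The same gain as patients.** Ignoring the small slope cost, the equivalent unadjusted size is 30 / (1 − rho²): 31.2 per arm at rho 0.2, 33.0 at 0.3, 40.0 at 0.5.

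**5. A smaller true effect.** At d = 0.6 the same formulas give 62.8% unadjusted, 66.1% at rho 0.3 and 74.4% at rho 0.5.

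**6. Chance imbalance.** The SE of the difference in early-trough means is 0.258 SD, so a difference above 0.5 SD in either direction arises in 5.3% of trials. Given such a difference, the unadjusted estimate shifts by rho × 0.5 SD: 0.15 SD at rho 0.3, 0.25 SD at rho 0.5. This is not a second benefit to add to step 2, since the unadjusted standard error already includes this variation.

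**The case against.** The strongest reply is that nothing is wrong: after 1:1 randomization the unadjusted tests are unbiased and hold their overall type I error, and the plan already claims more than 90% power. That stands. A reader might infer from the chance-imbalance figures that the planned comparison is biased; the document does not support this, because the shift is conditional on one realized imbalance and averages to zero over randomizations.

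A second reply is that the gain is not demonstrated. Rho is nowhere given, and two or three troughs taken while tacrolimus is being started may predict later control poorly. That also stands. The protocol's emphasis on patient-to-patient variability, and its reliance on 72 hours of data for prediction, make some correlation plausible but do not quantify it. To call the gain free or certain would go too far.

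Third, a reader might infer that the early troughs are ignored altogether, or that they are necessarily a true baseline. Neither is established. If counting starts at transplant, those days are already inside the outcome, and adjusting would regress the outcome on part of itself. If allocation is known during the 72 hours (no blinding is described), early dosing could differ by arm. These gaps do not remove the point, but they must be closed before the adjustment can be used.

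Finally, CYP3A5 genotype may look like an obvious second covariate. Specific Aims, Sub-Aim 2 ties the pharmacokinetic and genetic work to a subset of patients, whereas the Research Plan genotypes each donor and recipient. Until these are reconciled, complete genotype data cannot be assumed.

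**Conclusion.** The point holds as a missed efficiency. The only comparison tests named are unadjusted, and readings that could sharpen the comparison are collected in both arms. At the effect 30 per arm detects with 90% power, the change runs from a loss of about half a power point (rho 0 to 0.05) to a gain of 6.0 points (rho 0.5), with break-even near rho 0.13. At rho 0.2 the gain is only 0.6 points.

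These figures rest on an assumed rho, a linear relation, similar variances in the two arms, and early troughs unaffected by allocation. They also read the Sub-Aim 2 tests as applying to Sub-Aim 1, which the cross-reference implies but Sub-Aim 1 does not itself say. The change is worth making because it costs so little; the trial's validity does not depend on it.

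**What to change.** In the Sub-Aim 1 Statistical Analysis, before any comparison by arm is seen:

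1. Count outcome days only after the 72-hour period, so that the baseline is not part of the outcome.
2. Analyse each drug-level outcome by a linear model with robust standard errors (or a rank-based equivalent) on arm plus one prespecified baseline: the mean distance outside the target range over the troughs from the first 72 hours, scored 0 when inside and using the same range as the outcome. Report the adjusted difference with its 95% CI, and keep the unadjusted test as a sensitivity analysis.
3. State either that dosing during the 72 hours is decided without regard to allocation or that allocation is revealed at 72 hours, so that the covariate is a true baseline.
4. Leave CYP3A5 genotype out of the model unless the two statements on who is genotyped are reconciled.

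The cost is a few sentences and one degree of freedom, with no new samples, visits or patients. The downside is about half a power point if rho is near zero.

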We have developed a powerful platform that utilizes patient clinical data to construct a Parabolic Response Surface (PRS). The PRS is patient-specific and based on individualized values that represent each patient's response to drug treatment. Examples of this response can be tacrolimus blood trough levels or quantitative markers of organ function or injury. PRS reconciles clinical data into a visual map that enables the immediate identification of optimal drug doses needed to bring drug levels to within the desired range. Importantly, because the PRS process does not require a priori knowledge of disease mechanism, it can efficiently prescribe precise and optimized drug doses despite the frequent changes to patient treatment regimens following transplantation that can have a profound effect on drug metabolism.

SPECIFIC AIMS:

Overall Aim: Prospective randomized clinical trial applying PPM to tacrolimus dosing in liver and/or kidney transplant recipients to show improvement in maintaining drug trough levels within the target range.

Sub-Aim 1: Prospective clinical trial comparing PPM-based dosing with standard of care physician guided dosing in liver and/or kidney transplant recipients to show improvement in time-within-target-range of drug trough levels.

Measures of drug level management will include i) fraction of days outside of target range, ii) fraction of days with large deviations (>2 ng/mL), and iii) ratio of area-under-the-curve outside of target range to total. Clinical measures in both arms will also be monitored to ensure subject safety and correlate trough level maintenance to clinical outcomes.

Sub-Aim 2: Substudy comparing the pharmacokinetics of patients with high variance in tacrolimus dosing with those with low variance.

To examine contributors to variance in tacrolimus dosing, we will measure the pharmacokinetics of a subset of patients in this study and correlate the findings with donor/recipient genetics, changes in drug regimens, and clinical factors such as liver and kidney function. We will use the pharmacokinetic data to interpret the performance of PPM and provide additional validation for our trial.

RESEARCH PLAN:

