The aim of this project is to use PPM to uncover valuable and previously unknown information pertaining to patient dose requirements and correlate them with patient clinical and other contextual information. Importantly, because PPM is able to determine patient-specific levels of drug synergism and antagonism, this project is also expected to reveal vital patient subpopulation information in terms of how the modulation of multiple medications may impact tacrolimus levels and/or precision-based measures of immunosuppression at a patient-specific level. In addition, any future discovery of quantitative biomarkers as measures of immunosuppression will serve as a gateway towards even more effective personalized and relevant drug dosing.

Aim: Prospective randomized clinical trial applying PPM to tacrolimus dosing in liver and/or kidney transplant recipients to show improvement in maintaining drug trough levels within the target range.

Sub-Aim 1: Prospective clinical trial applying PPM to tacrolimus dosing in liver and/or kidney transplant recipients to show improvement in management of drug trough levels. This sub-aim constitutes the crux of the proposal. Its key objectives are: 1) to ensure the safety of the subjects; 2) to test the performance of PPM in guiding tacrolimus dosing in order to keep patient drug levels

within target range more frequently, lead to fewer days out of range, and result in smaller deviations from the target range than the standard of care.

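### Three unranked drug-level outcomes, with no primary, success rule or multiplicity rule, leave open what would show that PPM works; the power figure names no outcome and cannot be checked

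*Combined protocol and SAP*

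**What the plan says.** All references are to the combined protocol and SAP.

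- **Aim.** Specific Aims, Sub-Aim 1, sets out "to show improvement in time-within-target-range of drug trough levels".
- **Objectives.** Research Plan, Sub-Aim 1, wants PPM to keep levels "within target range more frequently, lead to fewer days out of range, and result in smaller deviations from the target range" compared with standard of care. The items are joined by a conjunction, but no rule says how many must be shown.
- **Outcomes.** The same section states: "Outcome measures will include i) fraction of days outside of target range, ii) fraction of days with large (> 2 ng/mL) deviations", followed by (iii), the ratio of area under the curve outside the range to total. Specific Aims gives the same three. Neither place ranks them.
- **Effectiveness analysis.** The Statistical Analysis paragraph of Sub-Aim 1 says effectiveness "will be assessed using area-under-the-curve and variance analysis as in sub-aim 1 above". That paragraph is itself part of Sub-Aim 1, and no such analysis is described before it. Variance is not one of the three outcomes.
- **Tests.** These appear only under Sub-Aim 2: "Similar to the previous sub-aim, comparisons between the two groups will be performed using either the two-tailed" Welch's or Student's t-test. For non-normal data, Levene's test is to compare variances and "a two-tailed Wilcoxon Rank Sum test will be used to compare medians". No test is tied to an outcome.
- **Power.** "Based on our preliminary results thirty patients per group will provide greater than 90% power", at alpha 0.05 in a two-tailed test.
- **Evaluable period.** "For the first 72 hours tacrolimus will be dosed per standard of care", in both arms. The plan does not say whether those days count in the outcomes.
- **Interim look.** The Data Safety Monitoring Plan compares outcome (ii) and biopsy-proven rejection at ten patients per arm. It gives no alpha or boundary.

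**The concern.** The Abstract says the trial aims to show that PPM is more effective than unaided dosing and that its data should justify a multi-center study. A reader of the result needs to know in advance which comparison carries that claim. Here the stated aim (time in range) and the stated analysis (area under the curve and variance) differ, and the outcome and test could both be settled after the data are seen.

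At stake are the false-positive rate behind the effectiveness claim and the meaning of the power figure. Nobody can tell whether the figure refers to time in range, the area ratio or variability. The ambiguity matters because the 4-versus-4 pilot in the Abstract is reported as significant for variability but only as a trend for reaching goal levels.

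**Working it through.** **Inputs from the plan.** 30 per group, 1:1, two-sided alpha 0.05, power above 90%, three outcomes. **Not in the plan:** difference, SD, correlations between outcomes. These are assumed below and shown as ranges.

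**1. The plan's own figure.** Power above 90% cannot be reproduced, because no effect size is given. It can only be solved backwards.

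- Normal approximation: d = (1.960 + 1.282) × √(2/30) = 0.84 SD.
- Noncentral t: d = 0.85 SD for 90% power.

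| True difference (SD) | t-test power, 30 per group | Wilcoxon power, normal data | Per group for 90% (t-test) |
|---|---|---|---|
| 0.85 | 90% | 88% | 30 |
| 0.70 | 76% | 74% | 44 |
| 0.50 | 48% | 45% | 86 |

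If the SD of the fraction of days out of range were 0.15 to 0.30 (assumed), 0.85 SD would be 0.85 × 0.15 = 13 to 0.85 × 0.30 = 26 percentage points. If the sentence meant a comparison of variances, an F-test on normal data needs a variance ratio of about 3.4 for 90% power. The figure is therefore attainable or not, depending on an input that is not given.

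**2. If any one outcome suffices.** Each outcome is tested two-sided at 0.05, so the nominal rate in PPM's favour is 2.5%. With three null test statistics of common correlation ρ, the rate is 1 − P(all three ≤ 1.96). At ρ = 0 this is 1 − 0.975³ = 7.3%, and two-sided 1 − 0.95³ = 14.3%. For other ρ, by simulation of correlated normal statistics:

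| ρ (assumed) | Any one, PPM's favour | Any one, two-sided | All three, PPM's favour |
|---|---|---|---|
| 0.4 | 6.6% | 13.1% | 0.1% |
| 0.5 | 6.3% | 12.5% | 0.2% |
| 0.7 | 5.5% | 10.9% | 0.4% |
| 0.9 | 4.2% | 8.3% | 1.1% |

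Zero correlation is implausible for three summaries of the same daily troughs, so 0.4 to 0.9 is the relevant range. As a check, all three outcomes were computed from simulated shared troughs in eight settings. All settings were assumed: 5 to 14 daily troughs, within-patient SD 2 or 3 ng/mL, target half-width 1 or 2 ng/mL. Pairwise correlations were 0.37 to 0.75. The any-one rate in PPM's favour was 4.6% to 5.6% with Welch's test and 4.8% to 5.7% with Wilcoxon. Outcome (i) alone with Welch's test gave 2.3% to 2.6%, as it should. None of these rates counts the variance analysis or the choice among tests.

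**3. If all three must succeed.** The false-positive rate with no effect on any outcome is in the last column above. Joint power depends on the power of each test:

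- 90% each: 78%, 81% and 85% at ρ = 0.5, 0.7 and 0.9.
- 97% each (about 1.01 SD): at least 1 − 3 × 0.03 = 91% at any correlation; 92.6% at ρ = 0.5 and 95.1% at ρ = 0.9.

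**4. What a 4-versus-4 pilot can support.** If such a pilot had observed exactly 0.85 SD, the 95% confidence interval (noncentral t, normality assumed) would be about −0.64 to 2.28 SD.

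**The case against.** Four arguments on the other side have weight.

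- **There is a lead outcome in practice.** The aims all concern staying in range, and outcome (i) is the direct complement and is listed first. This stands as a reason to choose (i). It does not settle the matter, because the outcome is never designated primary and the effectiveness sentence points to area under the curve and variance.
- **Silence is not permission.** A reader might infer that the plan allows a claim on any single p < 0.05. It does not say so, and the conjunction in the objectives leans towards a joint reading. This stands: the any-one rates are conditional on a rule that the plan neither states nor excludes.
- **The trial has not been shown to be underpowered.** A reader might infer that 30 per group is too few, or that a joint rule must push power below 90%. Neither follows. The pilot is described as published and may support the figure, and joint power stays above 90% if each test has about 97%. This stands in full.
- **A confirmatory study is to follow, and these are drug-level outcomes.** This limits the harm and lowers the severity. It does not remove the point, since this trial is meant to show effectiveness and to justify that study.

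**Conclusion.** The point holds as a should-fix. The plan fixes no primary outcome, order, success rule or multiplicity rule; its aim and its effectiveness analysis do not match; and its tests are not assigned to outcomes.

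The size depends on the rule. If one outcome suffices, the false-positive rate in PPM's favour is about 4.2% to 6.6% instead of 2.5%, for assumed correlations of 0.9 to 0.4 and before counting the variance analysis or the choice among tests. If all three are required, it is about 1% or less, with joint power of 78% to 85% only when each test has exactly 90% (correlations 0.5 to 0.9).

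The power figure cannot be checked as written. It is correct for a t-test if the true difference on the intended outcome is about 0.85 SD or more. Its incompleteness alone would be a reporting gap; together with the unranked outcomes, it leaves the trial's criterion of success undefined.

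**What to change.** 1. Name outcome (i), the fraction of days outside the target range, as the single primary outcome, to match the Sub-Aim 1 aim. Count only days after the 72-hour period in which both arms receive standard dosing.
2. Test it two-sided at 0.05 with one test chosen in advance from those under Sub-Aim 2, for example Welch's t-test with Wilcoxon as a sensitivity analysis.
3. Make (ii), (iii) and the variance analysis secondary in one pre-stated fixed order, each tested at 0.05 only if the one before is significant, or label any of them exploratory. The order and the status of the variance analysis are the sponsor's choice.
4. State that the interim comparison of (ii) is for safety only and supports no efficacy claim, or account for its alpha.
5. Restate the power sentence for (i): 30 per group gives [x]% power ([test], two-sided 0.05) for a difference of [d] percentage points, SD [y], from [source]. Add that a 4-versus-4 pilot estimates the effect very imprecisely. If the supportable effect is below about 0.85 SD, keep 30 per group and lower the stated power (76% at 0.70 SD, 48% at 0.50 SD).

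**Cost.** Mainly wording, with no change to the sample size. The stated power may fall, possibly by a good deal; holding 90% instead would take 44 per group at 0.70 SD or 86 at 0.50 SD. A result on (ii), (iii) or variability alone could no longer carry the effectiveness claim.

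### Sub-Aim 2 compares undefined high- and low-variance groups with unadjusted tests; one pre-defined continuous variability value per patient, adjusted for arm, would use the same data better

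*Combined protocol and SAP*

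**What the plan says.** The Research Plan titles Sub-Aim 2 "Comparing the pharmacokinetics of patients with high variance in tacrolimus dosing with those with low variance", and the Specific Aims describe it in nearly the same words. Neither place says how variance is measured, over which days, or where high ends and low begins. Variance in dosing could mean the doses given or the trough levels reached.

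The statistical paragraph under Sub-Aim 2 says: "Similar to the previous sub-aim, comparisons between the two groups will be performed", by t-test or, for non-normal data, by rank test, and that "a two-tailed Levene's test will be used to compare variances". No covariate is mentioned.

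The same sub-aim will also "correlate the findings with donor/recipient genetics, changes in drug regimens, and clinical factors such as liver and kidney function". The findings here are the PK results.

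On who is sampled, the Specific Aims say "we will measure the pharmacokinetics of a subset of patients in this study". The Research Plan says "For each subject, at least three blood samples (pre-dose and 2 and 6 hours after the dose) will be collected on study days", and names three days (the second, seventh and fourteenth).

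On timing, Sub-Aim 1 states: "For the first 72 hours tacrolimus will be dosed per standard of care". PPM guidance starts after that, in one arm only.

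**The concern.** Sub-Aim 2 is how the plan intends to learn why some patients vary more than others, and its PK data are meant to help interpret how PPM performs. Three things weaken it.

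- **The groups are undefined.** The cut-off and even the variable could be chosen after the data are seen.
- **A continuous quantity is split in two.** This usually discards information. No other planned analysis recovers it, because the correlations relate PK to genetics, drug regimens and organ function, not to a per-patient variability value.
- **Arm is ignored.** PPM is intended to change how levels vary. If both arms are included, membership of the high group and PK exposure on days 7 and 14 may both carry an arm effect. An apparent link between PK and variability could then partly restate the randomized comparison.

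A real link would be easiest to miss if only a subset is sampled.

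**Working it through.** **Inputs.** From the documents: 30 patients per arm (60 in all), 1:1 allocation, two-sided alpha 0.05, standard-of-care dosing in both arms for 72 hours, daily troughs until discharge. Assumed, because the documents give none: the PK–variability correlation r, the cut-off, the number of PK patients, troughs per patient, the spread of true SDs, and the arm effects.

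**1. The plan's own figure.** No power is stated for Sub-Aim 2. The figure of more than 90% belongs to Sub-Aim 1 and gives no effect size or SD, so it cannot be reproduced. At 30 per group, 90% power needs a standardized difference of (1.960 + 1.282) × √(2/30) = 0.84, or 0.85 using the t distribution. Nothing below disputes it.

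**2. What the tests compare.** If the two groups are the high- and low-variance patients, they are undefined. If they are the arms, which is what the previous sub-aim compares, the titled comparison has no stated test. The text needs repair on either reading.

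**3. Information lost.** For a linear relation and a normal measure, a median split has relative efficiency 2/π = 0.637, a loss of about 36%.

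**4. Power when r = 0.4 applies to the variability value as observed.** Fisher z approximation, with atanh(0.4) = 0.4236:

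- Continuous, arm-adjusted: Φ(0.4236 × √(N−4) − 1.96). N=60: Φ(1.21) = 0.89. N=30: Φ(0.20) = 0.58.
- Median split: r falls to 0.4 × √(2/π) = 0.319, with atanh 0.331, so power is Φ(0.331 × √(N−3) − 1.96). N=60: Φ(0.54) = 0.70. N=30: Φ(−0.24) = 0.40.

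Simulation (Welch test on the split against the arm-adjusted partial correlation) agrees:

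| N with PK | Median split | Continuous, arm-adjusted |
|---|---|---|
| 60 | 72% | 90% |
| 40 | 53% | 73% |
| 30 | 41% | 60% |
| 20 | 27% | 41% |

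At N=60, upper against lower third gives 80% and top quarter against the rest 62%. With r = 0.3 the pair is 46% v 65%; with r = 0.5 it is 91% v 98%.

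**5. Power when r = 0.4 applies to the true SD.** The observed log SD from m troughs has sampling variance of about 1/(2(m−1)), so r shrinks by the square root of the reliability.

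- m=5, true log SDs spread by 0.2: reliability 0.04/(0.04 + 0.125) = 0.24; r = 0.4 × √0.24 = 0.20.
- m=8, spread 0.4: reliability 0.16/(0.16 + 0.071) = 0.69; r = 0.4 × √0.69 = 0.33.

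Unequal stays weaken it further. In simulations over these ranges both powers fall well below the table, and the gain is roughly 0 to 16 points at N=60 and 2 to 11 at N=30. It is smallest when stays are short and unequal.

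**6. A step instead of a line.** If PK differs only by a step exactly at the median, the split does better: 83% v 72% at N=60, r = 0.4. A 25/75 cut would then give only 45%.

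**7. Arm effect.** Simulated with no PK–variability link within arms:

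| Arm shift in variability | Arm shift in PK exposure | Unadjusted split rejects, N=60 | N=30 |
|---|---|---|---|
| 0.85 SD | 0.5 SD | 8.8% | 7.1% |
| 0.85 SD | 0.8 SD | 16.0% | 10.2% |

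The arm-adjusted model rejects in about 5% throughout. With arm shifts of 0.5 and 0.3 SD the split rejects in only 5 to 6%.

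**The case against.** Several counter-arguments have force.

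- **The gain may be small.** This stands. The larger figures hold only if r refers to the noisy value actually observed. With few troughs per patient the advantage can nearly vanish. A reader might infer a fixed loss of 14 to 20 points; that range fits only the median split at r = 0.4 with a measure free of noise.
- **A split can win.** True for a step at the cut. The plan states no cut, so it cannot rely on this.
- **Arm bias needs large effects.** Also true. Day 2 sampling precedes PPM guidance, and parameters from the planned compartment models need not move with exposure. The bias is possible, not established. Nor does a single arm term show whether the PK–variability slope differs between arms.
- **The plan already has correlations.** It does, but not with variability.
- **It is a substudy.** Agreed. That limits the weight of the point, but the repair costs little.

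A reader might also infer that Sub-Aim 1 is invalid. Its effectiveness analysis "will be assessed using area-under-the-curve and variance analysis as in sub-aim 1 above" has no stated unit, and Levene's test run on pooled daily troughs would ignore correlation within patients. The documents do not support that inference. Nothing applies Levene's test to pooled troughs; it is named only under Sub-Aim 2, for non-normal data. The three listed Sub-Aim 1 outcomes each give one value per patient. What is missing there is a detail of wording.

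**Conclusion.** The point holds as a low-cost improvement to a secondary aim. The documentary gaps are certain: no variability measure, window or cut-off, an ambiguous pair of groups, no arm term, and an unclear number of patients with PK sampling. The direction of the power gain is reliable for a roughly linear relation and a reasonably well-measured variability value. Its size is not: about 18 or 19 points if r = 0.4 holds for the observed value (90 − 72 at N=60, 60 − 41 at N=30), but possibly close to nothing with short, unequal stays. False-positive rates of about 7 to 16% arise only if PPM strongly shifts both variability and PK exposure; with modest arm effects the bias is negligible. All of these figures rest on assumed correlations, arm effects and trough counts.

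It would go too far to read this as a flaw in the main comparison. Sub-Aim 1's outcomes, its 30 patients per group and its stated power are untouched.

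**What to change.** Replace the high/low comparison with wording such as: *Each patient has one pre-defined continuous variability value, the log within-patient SD of [dose or trough, to be stated] after hour 72, corrected for the number of values. It is related to each pre-named PK parameter or genotype, one at a time, in a linear model adjusted for arm. All results are reported.*

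Also:

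- Say which two groups the named t, rank and Levene's tests compare, if any of these tests are kept.
- Reconcile the subset in the Specific Aims with the each-subject wording in the Research Plan, and state the number of patients with PK sampling.
- Keep the planned correlations with genetics, drug regimens and organ function.
- Do not enter all predictors together in a small sample. In the error-free case with r = 0.4 and N=20, seven added terms cut power to 25%, below the 27% of the median split.
- For Sub-Aim 1, at most add one sentence: if any variance is compared between arms, the patient is the unit. No further model is needed.

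The cost is wording and a simple model, with no new samples. The drawbacks are several tests instead of one, predictors that overlap and are not separated, an assumed linear shape with a common slope in both arms, and a noisy measure when stays are short.
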